However, by nature, 3 tests will be performed for each subject unless they experience death or are unable to perform one (or more) test during the follow-up. The repeated nature of the data will be considered including a random effect in the analyses. We will construct a logistic regression model with hemodynamic criteria for intermediate risk or high-risk status as outcome and cMRI dichotomous variable as exposure using a random effect at the patient level (2). The glmer command from the lme4 package will be used (R package, CRAN). Sensitivity and specificity and their confidence interval will then be extracted from the logistic model.

This analysis will consequently provide the overall (i.e. across the 3 time-points) sensitivity and specificity of cMRI integrated aforementioned exposition variable for the integrated aforementioned RHC definition taking into account the repeated nature of the data.

In addition, the following secondary analyses will be performed:

- sensitivity and specificity evaluation of cMRI integrated exposition variable for the integrated RHC at each time points (i.e. at baseline, 3-6 months and 24 months),
- sensitivity and specificity evaluation for each component of the RHC definition (i.e. considering only cardiac index $< 2.5 \text{ l/min/m}^2$ or only right atrial pressure $> \text{ or } = 8 \text{ mm Hg}$) and cMRI definition (i.e. considering only cMRI CI $< 2.5 \text{ l/min/m}^2$ or only RVEF $< 35\%$ or only absolute decrease of 10% of RVEF at a follow-up evaluation) overall and at each time-points.

In addition, parametric or non-parametric correlation analyses (depending on variable distributions) will also be performed for cMRI CI and RHC CI.

IV/ Analyses of Secondary objectives

Secondary objectives 1 and 2:

- 1) To assess the predictive value of the first occurrence of morbimortality events in 2 different analyses derived from RHC criteria (cardiac index (CI) $< 2.5 \text{ l/min/m}^2$ or a right atrial pressure $= \text{ or } > 8 \text{ mm Hg}$) and from cMRI criteria (CI $< 2.5 \text{ l/min/m}^2$ or RVEF $< 35\%$ or an absolute decrease of 10% of RVEF at a follow-up evaluation).
- 2) To assess the univariable association between first morbimortality events occurrence and NYHA functional class, 6-minute walk distance, plasma level of BNP/NT-proBNP, and continuous hemodynamic variables from cMRI, RHC and echocardiography data collected at baseline and after 3-6 months of follow-up.

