The morbimortality event will be defined as the composite endpoint of

- 1 Death from any cause
- 2 Lung transplantation
- 3 Atrial septostomy
- 4 Worsening of PAH defined by all three following criteria: a decrease in the 6-minute walk distance of at least 15 % from baseline (or unable to perform the test), a worsening of PAH symptoms and an unscheduled hospitalization (or an increase in the length of stay in the hospital) due to PAH

The following exposition variables will be used:

- RHC and cMRI definition used in the primary analysis
- Components of the RHC and cMRI definitions
- Additional RHC variables: stroke volume index, mean pulmonary arterial pressure, pulmonary vascular resistance, SvO_2 , pulmonary arterial compliance (stroke volume divided by pulse pressure)
- Additional cMRI variables: stroke volume index, right ventricular end-systolic volume index, right ventricular end-diastolic index, right ventricular end-systolic volume divided by stroke volume as an estimate of right ventriculo-arterial coupling
- Echocardiography variables: pericardial effusion, TAPSE $< 18 \text{ mm}$, right atrium area $= \text{ or } > 18 \text{ cm}^2$.

Proportional hazard analysis

Association between factors and time to first occurrence of events will be assessed using Cox proportional hazard regression. Both univariable and multivariable analyses will be performed. The validity of the assumptions of the Cox models will be checked: proportional hazards, log-linearity, absence of interaction and collinearity.

The adjusted analyses will be adjusted for NYHA class, 6-minute walk distance and natriuretic peptides. Additional adjustment factors found significant will also be entered in a multivariable analysis after stepwise forward-backward selection using a 0.05 threshold.

Importantly, the aforementioned RHC and MRI definitions will be first used as exposition variables.

In addition, the components of each definition and additional cMRI variables will also be used as individual exposition variables.

Associations between echocardiography variables and outcome will also be evaluated.

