Internal validation of the multivariable model and of the score which could be derived from it will be performed using the bootstrap method described by Harrell *et al* (8). Importantly, variables will be used both as dichotomized variables (using the cut-offs used in the primary objective) and as continuous variables. In case a continuous variable should be dichotomized for lack of log-linearity, the cutpoint will be validated in the same bootstrap resamples as for the model and score. In addition, optimal cutpoints will also be assessed on the continuous variables based on C-index maximization (9).

Secondary objectives 4:

4) To quantify complications due to cMRI and to RHC.

This will be mostly a descriptive analysis. The overall frequency of reported adverse events and severe adverse events will be compared between groups using the Chi-Square test (or Fisher's exact test where requested). In addition, to account for the paired nature of the data, a McNemar test will be performed.

Secondary objectives 5:

5) To determine the magnitude of better tolerability of cMRI over RHC for the patient.

Physical and psychological distress due to cMRI and RHC will be measured with questionnaires.

The comparison of the Likert-type scales of the questionnaires will be carried out using the Chi-Square test.

Secondary objective 6:

6) To create a biobank for diagnosis and prognosis purposes This study is a prospective cohort study. PAH patients will be recruited in 20 centers of the French network of severe pulmonary hypertension.

Blood samples to obtain DNA at one visit from circulating blood cells and plasma at all visits with MRI.

References

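### Secondary objective 2 is set on continuous echocardiography variables, but the SAP's exposure list enters TAPSE and right atrium area only as cut-offs

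*SAP*

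**What the plan says.** All of this is in SAP section IV.

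- **Secondary objectives 1 and 2, statement of objective 2.** Univariable association is to be assessed between first events and clinical markers together with "continuous hemodynamic variables from cMRI, RHC and echocardiography data collected at baseline and after 3-6 months of follow-up".
- **Same heading, list of exposition variables.** The echocardiography line begins "Echocardiography variables: pericardial effusion, TAPSE" and fixes TAPSE at below 18 mm and right atrium area at 18 cm² or more. The other lines include "Additional RHC variables: stroke volume index, mean pulmonary arterial pressure, pulmonary vascular resistance" and "Additional cMRI variables: stroke volume index, right ventricular end-systolic volume index, right ventricular end-diastolic index", with no thresholds.
- **Proportional hazard analysis.** The order of work is that "the aforementioned RHC and MRI definitions will be first used as exposition variables"; those definitions are yes/no composites. Echocardiography is to be examined for association with outcome, with no scale stated. Log-linearity is among the Cox assumptions to be checked.
- **Secondary objective 3.** Candidates for the stepwise model are those of objectives 1 and 2, and "variables will be used both as dichotomized variables (using the cut-offs used in the primary objective) and as continuous variables".

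**The concern.** The list of exposures is what a programmer will follow. For echocardiography it does not deliver what objective 2 describes: two measured quantities appear only as yes/no variables, and the third entry is pericardial effusion.

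Two things are at stake. First, the univariable associations for TAPSE and right atrium area would be estimated with less information than the measurements contain. Second, objective 3 draws its candidates from the same list, keeps only those with p < 0.05, and plans a prognostic score from the result. If the two variables enter only as cut-offs, the coding itself makes them more likely to drop out. Cutting in advance also bypasses the SAP's own sequence, in which log-linearity is checked and a continuous variable that fails is dichotomized, with the cutpoint validated in the bootstrap resamples. A variable listed only as a cut-off cannot be checked for log-linearity.

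**Working it through.** **Step 1. The text, side by side.**

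| Place in the SAP | Form of TAPSE and right atrium area |
|---|---|
| Objective 2, statement | Continuous, on the natural reading |
| Exposure list | Cut-offs only (< 18 mm; ≥ 18 cm²) |
| Proportional hazard analysis | Not stated |
| Objective 3, both-forms sentence | Not named; the cut-offs cited are those of the primary objective |

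Section III holds the primary-objective cut-offs. They concern RHC cardiac index, right atrial pressure, cMRI cardiac index and RVEF (level and absolute decrease). None is echocardiographic, so the objective 3 sentence does not say which cut-offs TAPSE and right atrium area would take, or clearly that it covers them. It also sits under objective 3 and does not amend the list for objective 2.

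**Step 2. Size of the loss.** The SAP gives no event count, power or distribution for these analyses, so there is no planned figure to reproduce. The following is illustrative.

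Assumptions, none from the SAP except the two-sided 0.05 level: the marker is normal, its effect on the log hazard is linear, and a proportion p lies on one side of the cut.

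- Information kept by the cut = φ(c)² / [p(1−p)], where c is the standard normal quantile of p.
- Events for 80% power, continuous marker = (1.960 + 0.842)² / (ln HR per SD)². At HR 1.5 this is 7.849 / 0.1644 = 47.7, so 48.
- Events for the cut-off form = the unrounded number divided by the information kept.
- Power of the cut-off form when the continuous form has 80% = Φ(2.802 × √(information kept) − 1.960).

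| Split | φ(c) | p(1−p) | Information kept | Events at HR 1.5 (48 if continuous) | Power (80% if continuous) |
|---|---|---|---|---|---|
| 50/50 | 0.3989 | 0.25 | 0.637 | 75 | 61% |
| 30/70 | 0.3477 | 0.21 | 0.576 | 83 | 57% |
| 20/80 | 0.2800 | 0.16 | 0.490 | 98 | 50% |
| 10/90 | 0.1755 | 0.09 | 0.342 | 140 | 37% |

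The ratio of events does not depend on the hazard ratio: it runs from 1/0.637 = 1.57 to 1/0.342 = 2.92. At HR 1.3 per SD, 115 events become 180 (50/50), 233 (20/80) or 334 (10/90). At HR 1.8, 23 become 36, 47 or 67.

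**Step 3. Discrimination.** In one simulation (3,000 subjects, exponential survival, no censoring), the C-index of a marker with HR 1.5 per SD was 0.60 continuous, 0.58 cut at the median and 0.55 cut at 20/80. With HR 1.8 it was 0.65, 0.60 and 0.57. Both hazard ratios are assumed.

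**The case against.** A reader might go further and infer that echocardiography is handicapped against cMRI and RHC in a comparison of modalities. The SAP does not support that, for three reasons.

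- The models whose C-index and NRI changes are compared contain covariates, RHC data and MRI data. None contains echocardiography. The SAP does assess a C-index for each model, so an echocardiography model may receive one, but no contrast with the other modalities is specified.
- The lead RHC and cMRI exposures are themselves dichotomous, and their components are written with cut-offs too. Only the additional RHC and cMRI variables are free of thresholds.
- The modalities do compete in the stepwise model of objective 3, but there the SAP uses variables in both forms. The bracketed reference to primary-objective cut-offs qualifies only the dichotomized form, so continuous use of TAPSE and right atrium area is a plausible reading.

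These points stand, and they limit the concern to the univariable analyses of objective 2 and an ambiguity in objective 3. They do not remove it: the objective 3 sentence names no echocardiography variable and does not reach objective 2.

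It can also be argued that the word continuous in objective 2 governs only the cMRI and RHC variables. The sentence allows this, but the reading is strained, and the plan would still be unclear on the point. Finally, these are supportive markers within one of six secondary objectives, which is a fair argument about weight. Objective 1 concerns RHC and cMRI criteria only, so nothing needs to change there.

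**Conclusion.** The concern holds in a limited form. The exposure list does not match objective 2 for TAPSE and right atrium area. Following the list would discard about 36% of the information at a 50/50 split, 51% at 20/80 and 66% at 10/90. These figures rest on a normal marker, a log-linear effect and assumed splits. Where the effect is far from log-linear the loss could differ, which is a reason to check before cutting. For objective 3 the coverage of these two variables is unclear rather than wrong. No handicap in a formal C-index or NRI comparison with cMRI or RHC is claimed, because none is planned. The primary analysis is untouched.

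**What to change.** 1. In the exposure list under secondary objectives 1 and 2, enter TAPSE (mm) and right atrium area (cm²) as continuous exposures for objective 2. Keep the existing cut-offs as secondary presentation and leave pericardial effusion as listed.
2. Under secondary objective 3, state that the rule of using both forms covers TAPSE and right atrium area, and that their dichotomized form uses the cut-offs already in the exposure list.

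The cost is two short edits and a few extra models. With two variables and the three planned sets of analyses (baseline, 3-6 months, time-dependent), that is 2 × 3 = 6 further univariable Cox models. Naming the continuous form as the main one avoids choosing between forms after seeing results. The change assumes that TAPSE and right atrium area are recorded as numbers and not only as above or below the cut-off, which the SAP does not say and the sponsor should confirm.

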Three sets of analyses will be provided. The first one will assess the association of baseline data with subsequent outcome, the second one will assess the association of 3-6 months data with subsequent and the last model will assess the association of baseline and 3-6 months data with outcome using a time-dependent Cox-model. In this time-dependant Cox model, association of baseline data will be considered until the 3-6 months data is acquired; association with outcome after the 3-6 months evaluation will be assessed using the 3-6 months data.

For each model, the predictive value will be assessed using C-index and NRI (3). In addition, changes in C-Index and NRI will also be evaluated comparing models including only covariates, including covariates and RHC data, including covariates and MRI data and including covariates, RHC and MRI data. This strategy has been used previously by our group (4).

Importantly, as sensitivity analyses,

- repeated events will be considering using a negative binomial model (5-7). This survival analysis will account for the occurrence of multiple events during the follow-up,
- the associations with the components of the composite endpoint will be assessed.

Secondary objective 3:

3) To assess the multivariable association between first morbimortality events occurrence and the above factors, identifying clinical and hemodynamic variables independently contributing to prognosis. Using the results of this analysis we plan to build a multiparameter prognostic score.

Two survival models will be used in this analysis, as mentioned above: Cox survival model (for first events) and negative binomial analysis as sensitivity analysis (accounting for repeated events).

Candidate variables for this analysis are the one mentioned for the analysis of secondary objective 1 and 2. A stepwise selection procedure will be used, retaining in the analysis only factor associated with a $p < 0.05$ with the outcome.

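### Gains in C-index and NRI from adding RHC, cMRI or both are reported from the fitting cohort with no stated optimism correction (minor; secondary objective)

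*SAP*

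**What the plan says.** SAP section IV, Secondary objectives 1 and 2 (Proportional hazard analysis), sets the performance measures: "For each model, the predictive value will be assessed using C-index and NRI (3" (the number is a literature reference). It then plans four Cox models. The first two are in "changes in C-Index and NRI will also be evaluated comparing models including only covariates, including covariates and RHC data", the other two in "including covariates and MRI data and including covariates, RHC and MRI data". No bootstrap, cross-validation or separate cohort is named for this comparison.

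On what enters as RHC or MRI data, the objective speaks of "To assess the predictive value of the first occurrence of morbimortality events in 2 different analyses derived from RHC criteria" and, in parallel, from cMRI criteria. The analysis text says that "the aforementioned RHC and MRI definitions will be first used as exposition variables" and that "the components of each definition and additional cMRI variables will also be used as individual exposition variables". The natural reading is one binary definition per modality at a time.

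Internal validation appears only under Secondary objective 3: "Internal validation of the multivariable model and of the score which could be derived from it will be performed using the bootstrap method". It is extended there to a cutpoint set for lack of log-linearity, and to nothing else.

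Three sets of Cox analyses are planned: baseline data, 3-6-month data, and a third in which "the last model will assess the association of baseline and 3-6 months data with outcome using a time-dependent Cox-model".

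**The concern.** A Cox model scored on the patients who supplied its coefficients looks better than it will in new patients, and each added term increases the flattery. The four-model comparison is the SAP's measure of how much RHC, cMRI and both improve prediction over clinical covariates. The combined model adds the most terms, so it gains most from the bias. A modality that adds nothing to the other can show a small positive gain, and the reader has no corrected figure to set beside it. The SAP accepts the need for correction under objective 3 but does not carry it over to this comparison.

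There is a separate, smaller point. NRI is planned for every model, including the time-dependent Cox model. NRI compares predicted risks from a fixed origin to a fixed horizon, and that model, whose exposure switches at the 3-6-month visit, does not supply such a risk.

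**Working it through.** **Nothing to reproduce.** The SAP gives no sample size, event count or expected gain, so the size of the bias has to be simulated under assumptions.

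**Inputs from the SAP.** Three base covariates (NYHA class, 6-minute walk distance, natriuretic peptides), one binary definition per modality, and the four models.

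**Assumed inputs.** N and event share of 100/20%, 180/20%, 180/30% and 300/40%, that is 20, 36, 54 and 120 events. Exponential survival, administrative censoring only, covariate log hazard ratios 0.5, -0.4 and 0.4, and definitions with 45% prevalence. Latent correlation between the definitions is 0 in rows a and b and 0.6 in rows c to e, because both contain a cardiac index criterion. NRI is the continuous form at the horizon. There were 600 replicates per setting, each with 60 bootstrap resamples and 2000 independent patients.

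**Formulae.** Optimism = value in the fitting sample - value of the same fitted models in new patients. Corrected value = apparent value - mean bootstrap optimism.

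| Case | Change in C: apparent | Change in C: new patients | NRI: apparent | NRI: new patients |
|---|---|---|---|---|
| a. One uninformative definition vs covariates | +0.0016 to +0.0078 | -0.0014 to -0.0074 | +0.08 to +0.18 | about 0 |
| b. Two uninformative definitions vs covariates | +0.003 to +0.0145 | -0.003 to -0.014 | +0.125 to +0.28 | about +0.01 |
| c. RHC real (log HR 0.7), cMRI adds nothing: both vs RHC | +0.0013 to +0.007 | -0.0013 to -0.006 | +0.065 to +0.20 | -0.01 to +0.02 |
| d. One strong definition (log HR 0.7) vs covariates, 54 and 120 events | 0.022 | 0.018 to 0.020 | 0.37 to 0.38 | 0.36 to 0.38 |
| d. The same, 20 events | 0.026 | 0.0155 | 0.38 | 0.32 |
| e. Two weak definitions (log HR 0.35 each) vs covariates | 0.017 to 0.027 | 0.002 to 0.013 | 0.33 to 0.39 | 0.22 to 0.30 |

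In row c the optimism in C lies between 0.0013 + 0.0013 = 0.0026 and 0.007 + 0.006 = 0.013. In row d it is 0.022 - 0.020 = 0.002 to 0.022 - 0.018 = 0.004 with 54 or 120 events, but 0.026 - 0.0155 = 0.0105 with 20. The 3-6-month analysis leaves out first events before that visit, so it has fewer events than the baseline analysis.

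**Second simulation, other assumptions** (150 patients/45 events, 200/40, 300/90; covariate log HR 0.4 per SD; RHC HR 3; 300 replicates). Adding an uninformative cMRI definition to RHC gave a change in C of +0.001 to +0.004 apparent against -0.001 to -0.004 in new patients, and an NRI of +0.03 to +0.14 against -0.03 to +0.02. One strong definition had optimism of 0.000 to 0.002 in C and about 0 in NRI. With 3 to 7 uninformative continuous variables per modality, optimism for the combined model rose to 0.025-0.097 in C and 0.22-0.49 in NRI.

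**RHC against cMRI.** Each adds one term, so this comparison is little affected when the two are of similar strength. With HRs of 3 and 1 and 90 events, optimism in C was 0.0013 for RHC and 0.0030 for cMRI.

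**Does the bootstrap help?** The corrected mean change in C is within 0.003 of the new-patient value from 180/20% upward and within 0.006 at 100/20%. For uninformative definitions it removes about 70% of the NRI bias and leaves +0.02 to +0.09. In rows d and e the corrected NRI is within 0.02.

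**Likelihood-ratio test in row c.** Both against RHC alone rejects in 4.8-6.2% of replicates (nominal 5%).

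**The case against.** A reader might infer that the plan would falsely conclude that cMRI adds to RHC. The document does not support that step. The SAP sets a two-sided 0.05 level, and the reference attached to C-index and NRI is, by its title in the SAP's list, an inference procedure for improvement in risk prediction with survival data. A claim of added value would ordinarily need a significant change, not just a positive one.

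Case c was also run with ordinary uncorrected bootstrap 95% intervals (300 replicates, 100 resamples). The change in C was falsely above 0 in 0-0.7% (Wald) or 0.3-1.7% (percentile) of replicates. NRI was falsely above 0 in 4.0-7.3% (Wald) or 3.3-5.0% (percentile). The NRI rates exceed the 2.5% expected in the upper tail. The Wald lower-tail rate was 0%, however, so the total is near 5%, with a Monte Carlo error of about 1.3 points. This is not the cited procedure, so it neither clears nor convicts it.

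A second tempting argument is the ranking. In case c the combined model has the highest apparent C-index in 56-69% of replicates, against 17-21% in new patients. But the SAP contains no rule that picks the model with the highest C-index, and the count treats third-decimal differences as wins. When both definitions truly matter (HR 2 each), the combined model is rightly best: 81-96% apparent, 83-97% in new patients.

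One could also read the bootstrap sentence as covering these models. Its place under objective 3 and its singular wording point the other way, and even then it would not say that the changes across four models are corrected.

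What stands: the reported gains are biased upward, and the SAP states no correction for them.

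**Conclusion.** The point holds as a bias in point estimates within a secondary objective. It is small when one strong, pre-specified binary definition is added with adequate events. It is larger for weak definitions, few events, several variables per modality, and the combined model. For an uninformative second modality the mean change in C is about +0.001 to +0.007 instead of a loss of similar size, and NRI is about +0.07 to +0.20 instead of about 0; the second simulation gave a lower NRI range, +0.03 to +0.14.

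All sizes rest on assumed sample size, event share, effects, correlation and NRI type. Stepwise selection and the time-dependent model were not simulated, so no size is claimed for them. An increase in false significant claims is not shown. The primary sensitivity and specificity analysis is unaffected. Severity: minor.

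**What to change.** 1. Extend the objective 3 bootstrap to the four-model comparisons, refitting all four models and repeating any stepwise step in each resample. Report the optimism-corrected change in C-index beside the apparent one. Do the same for NRI, noting that its correction is only partial when a marker carries little information. Present these as estimates, not as a selection rule: with two weak but real definitions, corrected C ranks the combined model first in 9-32% of replicates against 28-78% in new patients.
2. Base any claim that one modality adds to the other on the likelihood-ratio test between nested Cox models, fitted to the same patients with the same covariates. With one term per modality this is close to the test of that term in the combined model, so the change mainly states which test carries the claim.
3. Separately, compute NRI only for the baseline and 3-6-month models, stating its type and one horizon. The C-index may stay for the time-dependent model.

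The cost is SAP wording, some computing time and slightly less favourable reported gains. No new data are needed.

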EVITA

EVAluation of cardiac magnetic resonance Imaging (MRI) in follow up assessmenT of patients with pulmonary Arterial hypertension (PAH)
Prospective cohort study of *cardiac MRI in PAH*

STATISTICAL ANALYSIS PLAN

[name] / [name]

15th of December 2020

Sponsor: Centre Hospitalier Régional Universitaire de Nancy

Identifiers: NCT02845518 **Unique Protocol ID:** PHRC-15-0210

Principal Coordinator / Central Contact Person: [name] [name]

Methodologists and statisticians: [name] & [name]

I/ General considerations:

The 2-tailed significance level will set to $p < 0.05$.

II/ Descriptive analysis

Continuous variables will be expressed as mean \pm SD or as median (25-75 percentile) as appropriate. Categorical variables will be expressed as frequencies (percentages).

III/ Analyses to respond to main objective:

The aim of the trial is to assess the sensitivity and specificity cardiac magnetic resonance imaging (cMRI) regarding the diagnosis of hemodynamic criteria for intermediate risk or high-risk status determined from right heart catheterization (RHC) measurements. There will be 3 time-points: baseline, between 3 and 6 months and 24 months.

The outcome variable will consequently be hemodynamic criteria for intermediate risk or high-risk status defined as a cardiac index (CI) $< 2.5 \text{ l/min/m}^2$ or right atrial pressure $> \text{ or } = 8 \text{ mm Hg}$. This definition is in line with the last ESC/ERS guidelines for diagnosis and treatment of pulmonary hypertension (1).

The cMRI exposition variable will be defined as a cMRI CI $< 2.5 \text{ l/min/m}^2$ or a right ventricle ejection fraction (RVEF) $< 35\%$ or an absolute decrease of 10% of RVEF at a follow-up evaluation (for the second and third time-point).

Sensitivity, specificity and their exact 95% confidence intervals will be computed using the binomial distribution.

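### Objective 3 builds its score by p<0.05 stepwise selection from about 22 overlapping candidates without shrinkage, and does not say whether selection is repeated in the bootstrap

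*SAP*

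**What the plan says.** All references are to the SAP.

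- **Level (section I).** "The 2-tailed significance level will set to" p<0.05.
- **Candidate pool (section IV, Secondary objective 3).** "Candidate variables for this analysis are the one mentioned for the analysis of secondary objective 1 and 2".
- **Selection rule (same place).** "A stepwise selection procedure will be used, retaining in the analysis only factor associated with a" p below 0.05 with the outcome.
- **What the pool holds (Secondary objectives 1 and 2).** It has the clinical variables "NYHA functional class, 6-minute walk distance, plasma level of BNP/NT-proBNP" and a list of exposure variables. That list opens with "RHC and cMRI definition used in the primary analysis", continues with the components of those definitions, and adds further RHC, cMRI and echocardiography measures, among them "right ventricular end-systolic volume divided by stroke volume as an estimate of right ventriculo-arterial coupling".
- **Adjusted Cox models (Secondary objectives 1 and 2).** These are adjusted for the three clinical variables and use "stepwise forward-backward selection using a 0.05 threshold" for further covariates. The Cox assumptions are to be checked, collinearity included.
- **Validation (Secondary objective 3).** "Internal validation of the multivariable model and of the score which could be derived from it" is to be done by a bootstrap method given by citation. Variables are used dichotomised, at the primary-objective cut-offs, and also as continuous. A cutpoint needed because log-linearity fails is validated within the same resamples. Further cutpoints are sought by maximising the C-index, with no resampling mentioned for that step.

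The section gives no rule for choosing between forms of one measurement and no shrinkage of the score coefficients.

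**The concern.** Objective 3 has two products: a list of variables said to contribute independently to prognosis, and a score. Stepwise selection at a fixed significance level is a weak basis for both when candidates are many, overlapping and partly functions of one another. Which of several versions of the same information survives depends heavily on sampling variation. The survivors are those whose estimates happened to be large, so their coefficients are biased away from zero and their p-values are too small.

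The second issue is the performance figure. A bootstrap removes optimism only from the steps it repeats. If the selected variables are held fixed across resamples, the optimism due to selection stays in the corrected C-index. At stake are the credibility of the named predictors and the score's reported discrimination. The primary diagnostic analysis is not affected.

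**Working it through.** The SAP section on objective 3 gives no event count, C-index or other figure to reproduce, so the check counts the candidates and then simulates.

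**1. Candidate count** (section IV, objectives 1 and 2; one coding, one visit, NYHA class counted once)

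- Clinical: NYHA class, walk distance, natriuretic peptide = 3
- Integrated definitions: RHC, cMRI = 2
- Components: RHC CI, RAP, cMRI CI, RVEF, RVEF decrease = 5
- Additional RHC: SVI, mPAP, PVR, SvO2, compliance = 5
- Additional cMRI: SVI, RVESVI, RVEDVI, RVESV/SV = 4
- Echocardiography: effusion, TAPSE, right atrial area = 3

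Total: 3 + 2 + 5 + 5 + 4 + 3 = 22. At baseline it is 21, because the RVEF decrease exists only at follow-up. It is more if both codings or both visits enter. With an assumed 40 to 120 events, that is 40/22 = 1.8 to 120/22 = 5.5 events per candidate.

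**2. Overlap**

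- With A = low RHC CI and B = raised RAP as 0/1 indicators, the RHC definition is D = 1 - (1 - A)(1 - B) = A + B - AB. It carries nothing beyond its components; entered with A and B, it acts as their interaction with the sign reversed. The cMRI definition is determined by its components in the same way.
- CI and SVI each appear twice, from RHC and from cMRI.
- If cMRI stroke volume is the RV volumetric one (the SAP does not say), then SVI = RVEDVI - RVESVI, and RVESV/SV = (RVEDV - SV)/SV = 1/RVEF - 1. These are exact functions of other candidates.

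**3. Simple reference figure**

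For 22 independent candidates, all unrelated to outcome, the expected number of false selections is 22 x 0.05 = 1.1, and P(at least one) = 1 - 0.95^22 = 0.676. This is a benchmark only, since the real candidates are neither independent nor all null.

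**4. Simulation** (all settings assumed)

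Forward-backward Cox selection at p<0.05, 22 candidates, pairwise correlation 0.3, true C-index taken in 2,500 new patients.

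- Setting A: N = 200, 3 real predictors with log-HR 0.35 per SD, 60 data sets, 25 resamples each.
- Setting B: N = 150 (about 48 events) and N = 300 (about 100 events), 4 real predictors, 30 and 27 data sets, 12 resamples each.

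| Setting, events | Apparent C | Corrected, selection fixed | Corrected, selection repeated | True C | Models with a noise variable |
|---|---|---|---|---|---|
| A, 40 | 0.724 | 0.711 | 0.647 | 0.651 | 80% |
| A, 80 | 0.708 | 0.699 | 0.660 | 0.663 | 70% |
| A, 120 | 0.701 | 0.692 | 0.663 | 0.666 | 67% |
| B, about 48 | 0.74 | 0.73 | 0.67 | 0.68 | 80% |
| B, about 100 | 0.72 | 0.71 | 0.68 | 0.69 | 67% |

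Error with selection fixed (fixed minus true): A 0.060, 0.036, 0.026; B 0.05, 0.02. Error with selection repeated: A -0.004, -0.003, -0.003; B -0.01, -0.01.

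In setting A with no real predictor, 55-60% of runs still selected something. The corrected C-index was then 0.575 / 0.549 / 0.545 with selection fixed and 0.521 / 0.511 / 0.513 with selection repeated, against a true 0.500.

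The runs are few: the standard error of an 80% figure is sqrt(0.8 x 0.2/60) = 0.05 in A and sqrt(0.8 x 0.2/30) = 0.07 in B.

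**The case against.** A reader might infer that the validated C-index will be over-stated. The SAP does not support that. It plans a bootstrap by a cited method, it expressly places one data-driven step (the log-linearity cutpoint) inside the resamples, and it is silent on selection. Silence is not exclusion, the word model may be meant to cover the procedure that produced it, and the cited source is not at hand. This objection stands, and the C-index point is therefore conditional.

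Other points on that side:

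- **Collinearity is to be checked.** True, and objective 3 refers back to the same Cox model. But no action follows from the check, and it does not choose between a composite and its components.
- **One pool with every form is only one reading.** Definitions and components could be run in separate models, and the two codings could be two analyses. The text allows this but does not say so, and it takes the candidates for objective 3 from the whole list.
- **The numbers are assumed.** This stands. The 68% benchmark needs independent null candidates; with correlation 0.3 and no real predictor the figure was 55-60%. The simulations contain no composites, dual coding or cutpoint search, so they do not size those parts.
- **The three clinical variables are adjusted for under objectives 1 and 2 but compete under objective 3.** This may look like a contradiction. It is not: objective 3 asks which clinical and haemodynamic variables contribute, so letting them compete is a legitimate choice.
- **The objective is secondary and the score tentative.** True; it limits the weight of the point but does not remove it.

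**Conclusion.** The point holds in two parts.

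**Unconditional.** Followed as written, p<0.05 stepwise selection over about 22 overlapping candidates, with no shrinkage, will give an unstable set of predictors and inflated coefficients. Validation by bootstrap measures optimism in performance; it does not repair the list or the coefficients. Under the assumed settings (N 150 to 300, 40 to 120 events, correlation 0.3, three or four real effects), 67-80% of models kept at least one noise variable. Coefficient inflation follows from selecting on significance and was not sized separately.

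**Conditional.** The SAP does not state that selection, choice of form or the C-index-maximising cutpoints are repeated in each resample. If selection is not repeated, the validated C-index would be about 0.02-0.06 too high under the same assumptions with real predictors present. If it is repeated, the result is close to unbiased. The true size depends on the patient and event numbers and on the real correlations.

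This should be corrected before the score is built.

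**What to change.** Amend the text of Secondary objective 3 as follows.

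- **(a) Reduce the pool before selection.** Enter one form per measurement, and either a composite or its components, not both. Where stroke volume is the RV volumetric one, drop candidates that are exact functions of others.
- **(b) Validate the whole procedure.** State that selection, choice of form and both kinds of cutpoint are rerun in every bootstrap resample. Report the optimism-corrected C-index and calibration slope.
- **(c) Correct and qualify the score.** Multiply its coefficients by that bootstrap calibration slope, and report selection frequencies alongside the selected model.

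The cost is SAP wording, more computing time and a lower reported C-index. Forcing in the three clinical variables, or replacing stepwise selection by a penalised Cox model, is optional.
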